6.2. Effectiveness Endpoints

- Death (all-cause death, cardiovascular death)
- Cardiac function tests
- NYHA class
- Clinical effectiveness (as assessed by the physician)
- Laboratory tests (plasma brain natriuretic peptide [BNP], serum N-terminal pro-BNP [NT-proBNP])

6.3. Other Endpoints

Not applicable.

6.4. Covariates

Not applicable.

7. HANDLING OF MISSING DATA

If the severity, treatment, or outcome of an AE is missing, it will be regarded as having a value of "unknown" at the time of a statistical summarization.

If an observation for the dosing status, a safety endpoint, an effectiveness endpoint, or a laboratory test was done outside its time window (Appendices A1.1, A1.2, and A1.3), the obtained data will be regarded as missing data and will not be imputed.

Cleaning-uncompleted data will be basically handled as follows. Detailed handling of individual items will be explained in separate lists.

• Items for which data are missing: For both summarization and listing, their values will be handled as missing data (or "unknown" in the case of a categorical variable).

- Items for which data are inconsistent: For both summarization and listing, their values will be handled as missing data.
- Items for which signature is missing: For both summarization and listing, any data in a CRF with no signature of the contract physician (including when the CRF is signed only by individuals other than the contract physician) will be handled as missing data.

8. STATISTICAL METHODS AND ANALYSES

Unless otherwise stated, for patients who completed treatment, data within the first 52 weeks (364 days) + 30 days (= 394 days) will be included in each statistical analysis. For patients who discontinued treatment, data until the first visit after discontinuation of treatment with Selara tablets, or the date 30 days after the last treatment, whichever comes first, will be included. For patients who died, all data will be included.

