7.2.6. Observation period

7.2.6.1. Observation period

One year (52 weeks) from the start date of administration.

However, in patients who discontinue treatment with this drug, the period will be from the start date of administration to the first consultation day after the discontinuation day of treatment with this drug.

[figure not shown]

Figure 1. Observation Period for Each Booklet

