7.5.2. Rationale for sample size

Table 5 shows the number and proportion of cases of adverse events related to hyperkalaemia and renal impairment that occurred within 52 weeks (364 days) after the start of administration, for which a causal relationship could not be ruled out, in all CHF patients and patients with moderate renal impairment in the domestic Phase III study (Study A6141114) and the foreign Phase III study (Study EMPHASIS-HF).

Table 5. Adverse Events related to Hyperkalaemia and Renal Impairment that Occurred within 52 Weeks (364 Days) after the Start of Administration in Eplerenone Group for which Causal Relationship Could Not Be Ruled Out - Safety Analysis Set

Patients with moderate renal impairment eGFR < 50 mL/min/1.73m ²	All CHF patients
N=37	N=111
2 (5.4)	3 (2.7)
0	1 (0.9)
1 (2.7)	1 (0.9)
N=224 a	N=1360
20 (8.9)	56 (4.1)
1 (0.4)	4 (0.3)
6 (2.7)	12 (0.9)
	impairment eGFR < 50 mL/min/1.73m ² N=37 2 (5.4) 0 1 (2.7) N=224 a 20 (8.9) 1 (0.4)

n (%)

In Study A6141114, the ratio of patients with moderate renal impairment to all CHF patients in Japanese was 34.4% (76/221). Taking into account this result and the results of a Japanese epidemiological survey³), the ratio of patients with moderate renal impairment to CHF patients in Japan is estimated to be approximately 30%. Given that the target sample size of all CHF patients is 1000 patients, the number of patients with moderate renal impairment is expected to be approximately 300-350.

As shown in Table 5, the incidence rate of adverse events related to renal impairment for which a causal relationship could not be ruled out was 3.1% (8/261) in patients with moderate renal impairment in the combined results from Study A6141114 and Study EMPHASIS-HF conducted in CHF patients with systolic dysfunction in which the same primary endpoint (cardiovascular deaths or hospitalization due to heart failure) was compared to a placebo treatment group. Assuming that 3.1% is the true incidence rate of adverse events related to renal impairment for which a causal relationship cannot be ruled out in patients with moderate renal impairment, the expected number of cases of adverse events related to

^a: Including two patients with eGFR <30 mL/min/1.73m².

renal impairment for which a causal relationship cannot be ruled out is 9.3-10.9 when collecting 300-350 patients with moderate renal impairment.

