9.2. Reporting period

For each patient, the safety events reporting period begins at the time of the patient's first dose of this drug, and lasts through the end of the observation period of the study, which must include at least 28 calendar days following the last administration of a drug under study; a report must be submitted to Pfizer Safety (or its designated representative) for any of the types of safety events listed in the table above occurring during this period. If a patient was administered a drug under study on the last day of the observation period, then the reporting period should be extended for 28 calendar days following the end of observation.

If the investigator becomes aware of a SAE occurring at any time after completion of the study and s/he considers the SAE to be related to this drug, the SAE also must be reported to Pfizer Safety.

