For both Safety Analysis Set and Effectiveness Analysis Set, the following dosing data of Selara tablets will be summarized for the overall population and by eCLCr (<30 mL/min, 30 - <50 mL/min, ≥50 mL/min, unknown):

- Duration of treatment (continuous)
- Duration of treatment [for each of the periods defined in Appendix A1.1 (excluding the Final Visit)]
- Mean daily dose (continuous)
- Mean daily dose [for each of the periods defined in Appendix A1.1 (excluding the Final Visit)]

Reason for discontinuation [within 26 weeks: inadequate clinical response, AEs, others;
 after 26 weeks: inadequate clinical response, AEs, no revisit, others]

The duration of treatment is defined as the period from the first administration to the last administration in this study, including non-dosing periods. If the date of the last administration is unknown for a patient who discontinued treatment, the date on which the patient was first seen by the physician after the discontinuation will be considered as the date of the last administration.

• Follow-up Status

For the Effectiveness Analysis Set, the duration of follow-up (continuous) will be summarized. The duration of follow-up for a patient will be calculated as follows.

When the patient survived at Week 52,

Duration of follow-up = 52 weeks (364 days).

When the survival status of the patient is "unknown" at Week 52,

Duration of follow-up = date of final confirmation of survival – date of first administration in this study + 1 (days).

When the patient died by Week 52,

if the date of death is known,

Duration of follow-up = date of death - date of first administration in this study + 1 (days),

if the date of death is unknown.

Duration of follow-up = date of final confirmation of survival – date of first administration in this study + 1 (days).

• Estimated Creatinine Clearance (eCLCr) and Estimated Glomerular Filtration Rate (eGFR)

Scatter plots (x-axis: baseline eCLCr, y-axis: baseline eGFR) will be presented. The number of data and the Pearson product-moment correlation coefficient will be presented.

• Subgroup Analyses

For both Safety Analysis Set and Effectiveness Analysis Set, statistics will be presented according to Section 8.1 with respect to the following patient characteristics:

- Sex [male, female]
- Age [<15 years, 15 <65 years, 65 <75 years, ≥75 years]
- NYHA class [I, II, III, IV, not assessed/unknown]
- Diabetes mellitus with microalbuminuria or proteinuria [present, absent, unknown]

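### The SAP's default data window runs past Day 364, so adverse-event proportions, the crude death proportion and the person-year death rate can include events from beyond the 52 weeks they are meant to describe

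*SAP*

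**What the plan says.** The general rule in SAP section 8 has three parts, all subject to an opening proviso that other sections may state otherwise.

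- Completers: "for patients who completed treatment, data within the first 52 weeks (364 days) + 30 days (= 394 days) will be included" in every analysis.
- Discontinued patients: data to the first visit after stopping, "or the date 30 days after the last treatment, whichever comes first, will be included".
- Deaths: "For patients who died, all data will be included". No day limit is given.

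SAP 8.2.3 (safety analysis) sets no other cut-off for adverse events, adverse reactions or SAEs. It tabulates onset time by the windows of Appendix A1.1, whose Week 52 window runs from 267 to 394 days.

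Other parts of the plan stop at 52 weeks.

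- Protocol 7.2.6.1 defines the observation period as "One year (52 weeks) from the start date of administration".
- Protocol 7.3.8 collects adverse events on the CRF up to the last day of that period.
- Protocol 7.3.9 confirms survival status up to Week 52.
- Protocol 7.5.2 takes its planning rates from events "that occurred within 52 weeks (364 days) after the start of administration, for which a causal relationship could not be ruled out".
- SAP 8.2.2 sets follow-up for a patient alive at Week 52 as "Duration of follow-up = 52 weeks (364 days"). SAP 8.1.4 uses that time as the person-year denominator.

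Two protocol provisions do reach past Week 52. Section 7.3.5 accepts test results from the month after the observation period. Section 9.2 says that, for patients dosed on the last day, "the reporting period should be extended for 28 calendar days following the end of observation".

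**The concern.** A proportion presented as a 52-week incidence should count 52 weeks of events, and a rate should draw its numerator and denominator from the same period. Here the numerator can run on after the denominator, and the benchmark, have stopped.

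For adverse events the benchmark is Table 5, counted within 364 days. Protocol 7.5.2 expects the study to support evaluation of the safety profile alongside the clinical studies. A longer window can only raise the study's figure.

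For deaths the mismatch is inside one formula. A death dated Day 380 belongs to a patient who was alive at Week 52, so that patient contributes 364 days. Read literally, the death still enters the event count y and the crude proportion. The Kaplan-Meier estimate, read at one year, leaves it out. The crude proportion, the person-year rate and the Kaplan-Meier estimate are all intended for comparison with the domestic Phase III study and epidemiological surveys (Protocol 7.7), and they could rest on different windows.

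**Working it through.** **Inputs from the documents.** Planning rates in moderate renal impairment: 8/261 for renal impairment events and 22/261 for hyperkalaemia. In all CHF patients: 18/1471 and 59/1471. Sample sizes: 300 and 1000. One-year mortality in the two epidemiological comparators: 7.3% and 8.9% (Protocol 7.2.6.2). Windows: 364 and 394 days.

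**Assumptions, which the documents do not supply.** Full capture of events in the extra month; share of completers c between 0.5 and 1; constant hazard, or front-loaded onset as a Weibull with shape k = 0.5 or 0.3; for deaths, a tail of 30 days, because the SAP states no limit.

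**1. The plan's own figures reproduce.** 8/261 = 3.07%, 22/261 = 8.43%, 18/1471 = 1.22%, 59/1471 = 4.01%. With p ± 1.96·√(p(1−p)/300), 3.1% gives 1.14%-5.06% and 8.4% gives 5.26%-11.54%, matching the protocol's 1.1%-5.1% and 5.3%-11.5%. These are already 364-day rates, so a Day 364 cut-off changes none of them.

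**2. Extra time.** 30/364 = 8.2%.

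**3. Event proportions at Day 394.** Constant hazard: p + c(1−p)[1 − (1−p)^(30/364)]. Weibull with c = 1: 1 − (1−p)^((394/364)^k).

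| 364-day rate | constant, c = 1 | constant, c = 0.5 | Weibull, k = 0.5 | Weibull, k = 0.3 |
|---|---|---|---|---|
| 3.1% | 3.35% | 3.23% | 3.22% | 3.17% |
| 8.4% | 9.06% | 8.73% | 8.72% | 8.59% |
| 1.2% | 1.30% | 1.25% | 1.25% | 1.23% |
| 4.0% | 4.32% | 4.16% | 4.16% | 4.09% |

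The relative rise is about 8% in the first case, about 4% in the second and third, and about 2.4% in the last. In the first case that is about 0.75 renal impairment and 2.0 hyperkalaemia patients per 300, or 1.0 and 3.2 per 1000.

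**4. Deaths.** With hazard h = −ln(1−p)/364, mean person-time to Day 364 is (p/h)/365.25 years. The matched rate is 100·p divided by that. The mixed rate puts 1 − exp(−394h) over the same person-time.

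| Mortality by Day 364 | Matched rate per 100 person-years | Mixed rate | Ratio | Crude proportion to Day 394 |
|---|---|---|---|---|
| 7.3% | 7.61 | 8.21 | 1.079 | 7.88% |
| 8.9% | 9.35 | 10.09 | 1.078 | 9.60% |

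This is 5.8 to 7.0 extra deaths per 1000 patients if everyone completes and every late death is captured.

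**5. Kaplan-Meier.** SAP 8.1.4 reads the estimate at one year, and a death after Day 364 does not alter it. SAP 8.2.4.1 handles undated deaths first learned of after Week 52 as alive at the last survival confirmation or at Day 364.

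**The case against.** **Deaths.** The SAP does partly state otherwise. Its follow-up rule recognises only deaths by Week 52, the Kaplan-Meier estimate stops at one year, and survival confirmation covers only the period to Week 52. This stands to the extent that few dated late deaths may be recorded. It also rules out a stronger reading, that all the death statistics, one-year mortality included, are inflated. But none of these provisions limits y or the crude proportion, and the default for patients who died is all data. A reader might also take Day 394 as the limit for deaths; that is the completers' rule, and deaths have their own rule without a limit.

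**Serious events.** A reader might infer that the extra month is observed mainly for serious events, because CRF collection ends with observation and the 24-hour form takes SAEs but no non-serious AEs (Protocol 9.1). The documents do not say this. Protocol 9.1 has all non-serious AEs recorded on the CRF. Protocol 7.3.5 accepts tests for a further month and sends clinically problematic changes to the adverse-event section whatever their seriousness. A tilt is possible but not established.

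**Rationale for 30 days.** The tail resembles the 28-day reporting extension and parallels the 30-day limit for discontinued patients. That explains including late safety data somewhere. It does not justify placing them in a 52-week proportion. It does show that cutting completers alone would create a new imbalance: a patient stopping on Day 360 could have events counted to Day 390, or to the first visit if earlier.

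**Consequence.** All tests are exploratory, no decision rule depends on these figures, and no formal test against Phase III adverse-reaction rates is planned. This stands and limits the weight of the point.

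**Conclusion.** The point holds as a mismatch between the SAP's default data window and the 364-day basis of the incidences, the planning rates and the person-time. Adverse-event and adverse-reaction proportions can take in onsets on Days 365-394. For deaths, the plan leaves y and the crude proportion open-ended while the person-time is capped.

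The upper bound of about 8% relative needs constant hazard, full capture, all patients completing and, for deaths, a 30-day tail. With half the patients completing, or with early onset, the rise is about 2%-4%, and incomplete capture makes it smaller still. Even the upper values of 9.06% and 3.35% lie well inside the planned ranges of 5.3%-11.5% and 1.1%-5.1%. The bias is small, but its direction is known and it is cheap to remove, so the SAP should be corrected.

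**What to change.** In SAP section 8 and Appendix A1.1:

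1. Keep the additional 30 days for tests and clinical evaluations only.
2. Count in the crude death proportion and in y only deaths dated on or before Day 364, to match the person-time and the Kaplan-Meier estimate. Take Day 1 as the date of first administration, as the follow-up formula already does.
3. For the 52-week incidences set against Table 5, count events with onset on Days 1-364 in all patients, so that a discontinued patient's 30-day tail is also cut at Day 364.
4. End the last A1.1 interval at Day 364 when it is used for onset time. The Week 52 window can still reach 394 days for measurements.
5. Put later events in the listing of adverse events outside the observation period, already planned in SAP section 9, and define that listing as starting after Day 364.

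The cost is a few sentences and a date filter. The downside is that a few late events move from the tables to the listing; none is lost.

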8.1. Statistical Methods

8.1.1. Continuous Variables

For a continuous variable, its summary statistics (n, mean, standard deviation [SD], median, maximum, minimum) will be presented.

8.1.2. Categorical Variables

For a categorical variable, patients included in each category will be summarized in terms of n and proportion (%).

8.1.3. Binary Variables

For a binary variable, patients included in each binary category will be summarized in terms of n and proportion (%). When a confidence interval (CI) of the proportion is presented, the two-sided 95% CI (exact method) will be presented.

When subgroups are compared with respect to proportion, the risk ratio (RR) and its 95% CI will be presented (See Appendix 2).

8.1.4. Time-to-event Data

Mortality at one year from the start of treatment will be estimated using the Kaplan-Meier method. Kaplan-Meier plots (displaying the number of at-risk patients every one month) will also be presented.

Analyses Based on the Person-Year Method

The incidence of an event per observation time will, if it is presented, be calculated using the formula:

Incidence (events/100 person-year) = $100 \times y/PT$ y: Number of events PT: Total observation time (years),

where the observation time is determined in conformity with the part "Follow-up Status" in "8.2.2. Patient Characteristics and Medical History". In addition, its 95% CI will be presented according to the formula ¹:

$$\left[\frac{100}{PT} \times \frac{1}{2} \chi_{2y}^{2}(\alpha/2), \frac{100}{PT} \times \frac{1}{2} \chi_{2(y+1)}^{2}(1-\alpha/2)\right]$$

y: Number of events

 $\chi^2_{2y}(\alpha/2)$: The $\alpha/2$ percentage point of the chi-square distribution of 2y degrees of freedom

8.2. Statistical Analyses

8.2.1. Patient Description

Constitution

Among the registered patients, the registered patients themselves, patients with their CRF locked/collected, patients included in the Safety Analysis Set, and patients included in the Effectiveness Analysis Set will be summarized in terms of number of patients. In addition, patients with their CRF uncollected, patients excluded from the Safety Analysis Set, and patients excluded from the Effectiveness Analysis Set will be summarized in terms of total number of patients and number of patients by reason of exclusion.

• Treatment Discontinuations and Dropouts

The number and proportion of patients who discontinued treatment will be presented by Visit (See Appendix A1.1) in the Safety Analysis Set and the Effectiveness Analysis Set. The number and proportion of patients who discontinued treatment will also be presented by reason of discontinuation.

• Patients Excluded from Analyses

Patients excluded from the Safety Analysis Set and those excluded from the Effectiveness Analysis Set will be presented in a tabular form with their reason for exclusion.

8.2.2. Patient Characteristics and Medical History

• Patient Characteristics

For both Safety Analysis Set and Effectiveness Analysis Set, statistics will be presented according to Section 8.1 with respect to the following patient characteristics:

- Sex [male, female]
- Age (continuous)
- Age [<15 years, 15 <65 years, ≥ 65 years, 65 <75 years, ≥ 75 years]
- Patient status at the first prescription [hospitalized, outpatient]

- Past hospitalization due to cardiovascular events (before receiving Selara tablets) [present, absent, unknown]
- Past hospitalization due to cardiovascular events (before receiving Selara tablets) [if present, predefined categories]
- Body height (continuous)
- Body weight (continuous)
- Body mass index (BMI) (continuous)
- Underlying cardiovascular disease [predefined categories]
- Duration of disease (continuous)
- Duration of disease [<5 years, 5 <10 years, ≥10 years, unknown]
- NYHA class [I, II, III, IV, not assessed/unknown]
- Reason of the administration of Selara tablets [predefined categories]
- Past history of device therapy [present, absent, unknown]
- Past history of device therapy [if present, predefined categories]
- Hepatic impairment (as assessed by the physician) [predefined categories]
- Renal impairment (as assessed by the physician) [predefined categories]
- Pregnancy [present, absent]
- Past history [predefined categories]
- Coexisting conditions [predefined categories]
- Pretreatments [predefined categories]
- Medications for CHF/hypertension [predefined categories]
- Estimated creatinine clearance (eCLCr) (continuous)
- eCLCr [<30 mL/min, 30 <50 mL/min, ≥50 mL/min, unknown]
- Estimated glomerular filtration rate (eGFR) (continuous)
- eGFR [$<30 \text{ mL/min}/1.73\text{m}^2$, $30 <50 \text{ mL/min}/1.73\text{m}^2$, $\ge 50 \text{ mL/min}/1.73\text{m}^2$, unknown]

A concomitant drug is considered as a pretreatment if the end date of its use coincides with the start date of administration of Selara tablets. A drug is not considered as a concomitant drug if the start date of its use coincides with the end date of administration of Selara tablets.

The Cockcroft & Gault formula will be used to estimate CLCr. The Japanese Society of Nephrology's formula will be used to estimate GFR.

• Dosing Status of Selara Tablets

For both Safety Analysis Set and Effectiveness Analysis Set, the following dosing data of Selara tablets will be summarized for the overall population and by eCLCr (<30 mL/min, 30 - <50 mL/min, ≥50 mL/min, unknown):

- Duration of treatment (continuous)
- Duration of treatment [for each of the periods defined in Appendix A1.1 (excluding the Final Visit)]
- Mean daily dose (continuous)
- Mean daily dose [for each of the periods defined in Appendix A1.1 (excluding the Final Visit)]

Reason for discontinuation [within 26 weeks: inadequate clinical response, AEs, others;
 after 26 weeks: inadequate clinical response, AEs, no revisit, others]

The duration of treatment is defined as the period from the first administration to the last administration in this study, including non-dosing periods. If the date of the last administration is unknown for a patient who discontinued treatment, the date on which the patient was first seen by the physician after the discontinuation will be considered as the date of the last administration.

• Follow-up Status

For the Effectiveness Analysis Set, the duration of follow-up (continuous) will be summarized. The duration of follow-up for a patient will be calculated as follows.

When the patient survived at Week 52,

Duration of follow-up = 52 weeks (364 days).

When the survival status of the patient is "unknown" at Week 52,

Duration of follow-up = date of final confirmation of survival – date of first administration in this study + 1 (days).

When the patient died by Week 52,

if the date of death is known,

Duration of follow-up = date of death - date of first administration in this study + 1 (days),

if the date of death is unknown.

Duration of follow-up = date of final confirmation of survival – date of first administration in this study + 1 (days).

• Estimated Creatinine Clearance (eCLCr) and Estimated Glomerular Filtration Rate (eGFR)

Scatter plots (x-axis: baseline eCLCr, y-axis: baseline eGFR) will be presented. The number of data and the Pearson product-moment correlation coefficient will be presented.

• Subgroup Analyses

For both Safety Analysis Set and Effectiveness Analysis Set, statistics will be presented according to Section 8.1 with respect to the following patient characteristics:

- Sex [male, female]
- Age [<15 years, 15 <65 years, 65 <75 years, ≥75 years]
- NYHA class [I, II, III, IV, not assessed/unknown]
- Diabetes mellitus with microalbuminuria or proteinuria [present, absent, unknown]

Estimated creatinine clearance (eCLCr)
 [<30 mL/min, 30 mL/min - <50 mL/min, ≥50 mL/min, unknown]

